8.3. Secondary endpoints

Related to secondary objective 1:

- 1- Genetic kidney- and immune-related risk factors measured as number of variants in kidney- and immune-related genes, associated to INS incidence, progression, and poor response to therapy.
- 2- A methylation profile of target genes measured as number of hypomethylated and hypermethylated immune-related gene regions, related to a faster progression to kidney failure and altered immune profile.

Related to secondary objective 2:

- 3- Difference in terms of % and absolute number of subpopulations of B cells and T cells among patients classified as SRNS/SDNS, IRNS, and healthy children.
- 4- Changes in immune cell subsets genes, expressed as the number of expressed genes per cell (log-transformed Unique Molecular Identifier counts, UMI), among patients classified as SRNS/SDNS, IRNS, and healthy children.
- 5- Signaling dynamics changes, measured as number of phosphosites for each target protein expressed in the subpopulation of primary B and T cells, implicated in the development of kidney damage in INS.

Related to secondary objective 3:

- 6- Difference in the urine EV concentration expressed as total number/urine creatinine levels, and size as mean diameter, among patients classified as SRNS/SDNS, IRNS, and healthy children.
- 7- Difference in the urine and serum EV surface proteome phenotype, in terms of the ratio of the average of label-free quantification intensities for each detected EV protein, among patients classified as SRNS/SDNS, IRNS, and healthy children.

Dipartimento Area Materno - Infatile

SC NEFROLOGIA E DIALISI PEDIATRICA – TRAPIANTI DI RENE – Direttore: [name]

[contact]

email: [contact]

8- Difference in the serum proteome, in terms of the ratio of average of label-free quantification intensities for each detected protein, among patients classified as SRNS/SDNS, IRNS, and healthy children.

Related to secondary objective 4:

9- To describe different molecular signatures (characteristics) for healthy children group in the same way done for the primary endpoint.

9. Enrollment and inclusion/exclusion criteria

The recruiting centers that will be involved in the study are listed in Appendix 1.

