Single cell RNAseq experiments combined with CITE-seq (collaborators involved: IRCCS Ca' Granda Ospedale Maggiore Policlinico and the University of Milano). CD3+ and CD19+ cells from peripheral blood will be sorted from purified PBMCs. CD3+ cells will be labeled using barcoded versions of anti-CD4 and anti-CD8 (TotalSeqC – Biolegend). After cell number and viability determination by automated cell count, the appropriate volume of CD3+ and CD19+ cells will be loaded onto a 10x Genomics chip to recover 10.000 cells/sample. RNA-Seq and single-cell repertoire analyses will be performed according to 10x Genomics 5' V(D)J protocol. Library sequencing will be performed using the Illumina NovaSeq 6.000 (Eurofins facilities, <https://eurofinsgenomics.eu/en/custom-dna-sequencing/>).

scRNA-Seq data analyses (collaborators involved: IRCCS Ca' Granda Ospedale Maggiore

Dipartimento Area Materno - Infatile

SC NEFROLOGIA E DIALISI PEDIATRICA – TRAPIANTI DI RENE – Direttore: [name]

[contact]

email: [contact]

Policlinico and the University of Milano). Raw fastQ files will be aligned to the human reference genome GRCh38, subjected to quality control filtering, and data normalization high variable genes will be identified and used in a principal component analysis (PCA). Downstream analyses of scRNAseq data on different unsupervised algorithms (UMAP, tSNE) will allow the spatial visualization of the single-cell dataset and features. T- and B- cell clusters will be defined using the Leiden algorithm, and differentially expressed genes (DEGs) between distinct cell clusters and experimental groups will be identified (P value ≤ 0.05 , log2 fold change ≥ 1.5). The procedure will generate an enrichment in immune cell subsets with a specific molecular signature that will be analyzed bioinformatically. Gene Ontology (GO) analyses will also be performed. For scTCR-seq and scBCR-seq data analysis, CDR3 sequences and V(D)J gene rearrangement will be obtained using the Cell Ranger VDJ 10X pipeline. T/B cells showing consistent CDR3 amino acid sequence will be defined as clonotypes.

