15.1 Primary endpoints: analysis

Statistical analysis using linear mixed effect models will ensure that data from the same individuals over time are properly considered. Network-based analysis using a linear mixed effect model LASSO implementation will allow us to identify key features associated with various clinical endpoints. To identify subsets of features, across all OMICs, associated with disease progression and treatment response, we will use a genetic algorithm-based feature selection approach. Unlike LASSO, this approach can identify non-linear relationships between features and can be linked to almost any predictive modeling approach. The feature subsets will further be evaluated in already available public domain data and then applied to a much larger cohort within the PRECISE consortium.

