15.2 Secondary endpoints: analysis

Differences between two groups of patients for all the analysis conducted will be evaluated using Student's parametric T-test (in case of normality of variables distribution and homoscedasticity of variance) or Mann – Whitney's non-parametric test. The normality of the data will be evaluated by the Shapiro-Wilk test and the homoscedasticity assumption of the variance will be evaluated by the Hartley F-max test. In cases where more features are available than samples, regularized regression approaches, such as LASSO, or feature selection approaches will be used to identify potential combinations of features associated with a given outcome. Analyses of differences in continuous outcome measures between 3 or more levels of categorical features will take place through analysis of variance (ANOVA) using multiplicity-adjusted post-hoc tests by Dunnett or Tukey, as appropriate. Data analysis will be performed using GraphPad Prism software and P-values of 0.05 will be accepted.

16. Quality control

Only after the approval from ethics committee and regulatory authorities, centers will enroll patients who meet inclusion and exclusion criteria and will propose them to participate to the study signing the informed consent. The coordinating center will have access to all registered data to verify any anomalies and report them to the participating center. All data will be handled, registered, and reported in accordance with the good clinical practice. As Promoter, Fondazione IRCCS Ca' Granda Ospedale Maggiore Policlinico can carry out a quality check on the study at its discretion. In this case, the investigator should allow the monitor to directly access all relevant documentation and devote some of his or her staff time to the reviewer to discuss the results of the monitoring and any other aspects of the study. In addition, the regulatory authorities can carry out inspections. In

Dipartimento Area Materno - Infatile

SC NEFROLOGIA E DIALISI PEDIATRICA – TRAPIANTI DI RENE – Direttore: [name]

[contact]

email: [contact]

this case, the investigator must authorize the inspector direct access to all relevant documentation and devote part of his time and his staff to the inspector himself to discuss the results of the monitoring and any other aspects of the study.

17. Study limitation

This study is a pilot study and shows some risks associated with it. The following limitations can be highlighted:

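### Secondary endpoint 4 uses a per-cell measure that does not show which genes change, and neither it nor the group DEG rule fixes the child as the unit of analysis or controls multiplicity

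*Protocol*

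**What the plan says.** Section 8.3 gives the aim of endpoint 4 as change in the genes of immune cell subsets, compared among SRNS/SDNS, IRNS and healthy children. The measure is "expressed as the number of expressed genes per cell (log-transformed Unique Molecular Identifier counts, UMI").

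Section 11 (single-cell RNA-seq) describes sorted CD3+ and CD19+ cells "loaded onto a 10x Genomics chip to recover 10.000 cells/sample". Cells are clustered by the Leiden algorithm, and then "differentially expressed genes (DEGs) between distinct cell clusters and experimental groups will be identified" by one rule, "P value ≤ 0.05 , log2 fold change ≥ 1.5". The section names neither the test nor the unit of analysis. It also gives no step that summarises cells by child and no multiplicity adjustment.

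Section 15.2 covers the secondary endpoints: "Differences between two groups of patients for all the analysis conducted will be evaluated using" a t-test or Mann-Whitney test, with ANOVA and adjusted post-hoc tests for three or more groups, and "P-values of 0.05 will be accepted". The only provision for correlated data is in section 15.1, repeated in section 17: "Statistical analysis using linear mixed effect models will ensure that data from the same individuals over time are properly considered".

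**The concern.** There are three problems.

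- **The measure does not match the aim.** The number of genes detected in a cell and the UMI count are different quantities, yet the text presents them as one. Both rise with sequencing depth and cell quality. A difference in the number of detected genes between groups says nothing about which genes changed, and it could reflect sample handling.
- **The nesting of cells within children is not addressed.** Cells from one child share that child's genetics, disease state, processing and batch, so information on a group difference grows mainly with the number of children. The mixed-model sentence covers repeated measures over time, not cells within a child. Schedule A lists mononuclear-cell blood at up to four time points (enrolment, 6 weeks, 12 months, first relapse), so one child may also contribute several correlated samples.
- **The DEG threshold is unadjusted.** An unadjusted P ≤ 0.05 is applied gene by gene and cluster by cluster. The adjusted post-hoc tests in section 15.2 deal with contrasts between groups, not with the number of genes. Read literally, the fold-change cut also keeps only one direction.

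At stake is whether reported class differences reflect the disease classes or a few children, a batch or sequencing depth.

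**Working it through.** The protocol states no power or false-positive rate for these comparisons, so there is no figure of its own to reproduce beyond the nominal 0.05.

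**Inputs from the protocol:** 10,000 cells per sample before clustering; P ≤ 0.05 and log2 fold change ≥ 1.5 (2^1.5 ≈ 2.8-fold); 110 incident patients and 40 controls (section 13).

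**Assumptions:** a two-sided test; intraclass correlation (ICC) of cells within a child; m cells per child per cluster; between-child SD τ of log2 expression; the group split; the number of children sequenced, which is not stated.

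**1. The P criterion alone, if cells are treated as independent.** Design effect DE = 1 + (m − 1) × ICC. True error = 2 × [1 − Φ(1.96/√DE)].

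| m | ICC | DE | 1.96/√DE | Error |
|---|---|---|---|---|
| 100 | 0.01 | 1.99 | 1.389 | 16% |
| 100 | 0.05 | 5.95 | 0.804 | 42% |
| 1,000 | 0.01 | 10.99 | 0.591 | 55% |
| 1,000 | 0.05 | 50.95 | 0.275 | 78% |

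With a smaller ICC of 0.001 the error is 6.2% at m = 100 and 16.6% at m = 1,000, so the size depends on both assumptions.

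A simulation of 20,000 runs at m = 500 and m = 10,000 agrees with the formula. At 55/55 children, m = 500 and ICC 0.01, the cell-level test rejects 42.3% of the time. With one mean per child, the error is 4.6% to 5.3% in every scenario run.

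**2. The joint DEG rule for a null gene, cells as unit.** The chance of passing both criteria is at most P(|difference| ≥ 1.5) = 2 × [1 − Φ(1.5/(τ√(1/n₁ + 1/n₂)))], taking equal cell numbers per child and enough cells for cell-sampling noise to be negligible.

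| Children per group | τ = 1 | τ = 1.5 | τ = 2 | τ at which 5% is reached |
|---|---|---|---|---|
| 55/55 | <0.001% | <0.001% | 0.008% | 4.0 |
| 70/40 | <0.001% | <0.001% | 0.015% | 3.9 |
| 10/10 | 0.08% | 2.5% | 9.4% | 1.7 |
| 5/5 | 1.8% | 11.4% | 23.6% | 1.2 |

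For example, at 55/55 with τ = 2 the standard error is 2 × √(2/55) = 0.381, 1.5/0.381 = 3.93, and the probability is 0.008%.

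**3. Uneven cell counts.** Pooling cells weights each child by its number of cells. With 55/55 children and lognormal cell counts per cluster (assumed SD of log count 1.5 to 2), simulation leaves about 13 down to 8 effective children per group. The chance of |log2 fold change| ≥ 1.5 for a null gene is then about 0.2% to 1.8% at τ = 1, 2.7% to 8.7% at τ = 1.5 and 8.6% to 19% at τ = 2. With an SD of log count of 1 it stays at or below 1.3%, even at τ = 2.

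**4. Multiplicity.** Even with the child as unit, 10,000 null genes (an assumed number) would give 10,000 × 0.05 = 500 with P ≤ 0.05 per contrast, before the fold-change cut.

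**The case against.** The strongest reply is that the protocol never makes cells the unit. Section 15.2 speaks of groups of patients, endpoint 4 is compared among classified patients, and a per-cell quantity can be averaged within each child before testing. How cells are aggregated is often left to an SAP, which is not shown. This stands as far as it goes: a reader might infer that cells are the unit and that DEG false positives are far above 5%, but the text does not establish either.

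Several further points also stand:

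- The fold-change cut is a strong filter at the planned group sizes.
- The 10,000 cells are per sample and before clustering. A figure of about 85% (m = 10,000, ICC 0.01) would need all of them in one test, which does not fit an endpoint about cell subsets.
- Comparing cell clusters within children is a different question from comparing groups.
- No passage says that DEG calls feed the primary signature. Section 15.1 selects features by LASSO and a genetic algorithm and then evaluates them in other data, so contamination of the primary result is a possibility only.
- The missing absolute-value bars may be shorthand.

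It can also be argued that the bracketed log UMI counts are meant per gene, which would be an expression measure. That may be the intention, but the words define a number of expressed genes per cell. An SAP should not have to replace an endpoint that the protocol has fixed. Nor does the SAP argument cover the DEG threshold, which the protocol itself sets without adjustment.

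**Conclusion.** The point holds for what the protocol fixes: a measure for endpoint 4 that does not match its aim, an unadjusted DEG threshold, and a correlation provision that omits cells within a child. It should be corrected, although it is not a demonstrated error in a planned test.

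The size is conditional. If cells were tested as independent, the P ≤ 0.05 criterion would have an error of about 16% to 78%, given ICC 0.01 to 0.05 and 100 to 1,000 cells per child per cluster. Endpoint 4 has no fold-change cut, so nothing would offset this. For the joint DEG rule the rate stays far below 5% at the planned group sizes with similar cell numbers per child. It exceeds 5% only if between-child spread is large and, in addition, few children are sequenced or cell counts are very uneven.

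**What to change.** - **Endpoint 4 (section 8.3):** redefine it as per-gene expression in each immune cell subset per child. Keep genes detected and UMI counts per cell as quality measures.
- **Unit (sections 11 and 15.2):** name the child as the unit for every group comparison. Either sum counts per child and cluster (pseudobulk) or fit a model with a child random effect. With pseudobulk, use one time point per test or add a child effect, so that repeat samples from a child are also covered.
- **DEG rule (section 11):** replace raw P ≤ 0.05 with FDR-adjusted P values, write the cut as |log2 fold change| ≥ 1.5, and state how many children are to be sequenced per group.

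The cost is protocol and SAP wording, and standard software does the analysis. The downside is that fewer genes will be called significant.

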15.1 Primary endpoints: analysis

Statistical analysis using linear mixed effect models will ensure that data from the same individuals over time are properly considered. Network-based analysis using a linear mixed effect model LASSO implementation will allow us to identify key features associated with various clinical endpoints. To identify subsets of features, across all OMICs, associated with disease progression and treatment response, we will use a genetic algorithm-based feature selection approach. Unlike LASSO, this approach can identify non-linear relationships between features and can be linked to almost any predictive modeling approach. The feature subsets will further be evaluated in already available public domain data and then applied to a much larger cohort within the PRECISE consortium.

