SC NEFROLOGIA E DIALISI PEDIATRICA – TRAPIANTI DI RENE – Direttore: [name]

[contact]

email: [contact]

that biomarkers obtained from liquid biopsies (blood and urine) will improve the stratification and prognosis of INS patients, allowing for accurate tailoring of treatments. As the pathogenesis of the disease is multifactorial, an integrated cellular and secretome multi-omics approach will allow for the identification of biomarkers across multiple levels, to be then validated in the routine clinical setting.

7. Objectives

The **PRIMARY OBJECTIVE** of the **PRECISE** study is the generation of a predictive model to differentiate children with SRNS or SDNS from patients with IRNS at the onset through the integration of -omics, genetic, and clinical data (biomarker signature).

The following **4 SECONDARY OBJECTIVES** will be pursued in the study:

1. Definition of the genetic/epigenetic modifications participating in the pathogenesis of INS.
2. Evaluation of adaptive immune system alterations in INS children.
3. Identification of specific protein patterns in serum and urine in different INS subtypes.
4. Description of the molecular characteristics in healthy children.

8. Methods

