8.1 Study design

Open, multicenter, non-pharmacological observational study.

[figure not shown]
Dipartimento Area Materno - Infatile

SC NEFROLOGIA E DIALISI PEDIATRICA – TRAPIANTI DI RENE – Direttore: [name]

[contact]

email: [contact]

Pediatric Idiopathic nephrotic syndrome

The PRECISE study is an open, multicenter, non-pharmacological biological study. The study will recruit a total of 310 INS patients and 40 controls. In details, the study will recruit 110 treatment-naïve childhood INS patients as a discover cohort, who will be followed for 12 months. At enrolment urine and blood samples will be collected as for normal clinical practice for the planned analysis. At the 12-month follow-up, patients will be classified according to international guidelines as steroid-dependent (SDNS)/frequent relapsing (FRNS) and infrequent relapsing nephrotic

Dipartimento Area Materno - Infatile

SC NEFROLOGIA E DIALISI PEDIATRICA – TRAPIANTI DI RENE – Direttore: [name]

[contact]

email: [contact]

syndrome (IRNS) (10). Additional assessments and biological samples will be performed according to the study flowchart and as described in the study procedure chapter. A homogeneous control group (n=40) by age of children undergoing sampling for minor urological surgical correction procedures will be also enrolled. In the validation phase, biological samples from an independent group of prevalent INS (200 cases) cases will be collected.

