8.2. Primary endpoint

To describe different molecular signatures (characteristics), predictive of the progression of INS, which would be able to discriminate among SRNS/SDNS and IRNS groups, based on genetic/epigenetic background, immune status, and vesicular proteome/transcriptomic profile.

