9.1 STUDY POPULATION (incident patients)

Inclusion criteria

1. Clinical diagnosis of idiopathic nephrotic syndrome (nephrotic range proteinuria uPr/uCr ratio > 2mg/mg, hypoalbuminemia < 3.0 g/dl, oedema);
2. No previous treatment for INS
3. age between 1 and 18 years at onset
4. signed informed consensus

Exclusion criteria

1. Congenital or infantile nephrotic syndrome (age < 1 year old); secondary nephrotic syndrome; glomerulonephritis; autoimmune diseases; vasculitis.
2. Absence of signed informed consensus
3. previous treatments with prednisone or prednisolone for INS

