10.1 Study visits

Population 1 (main population incident INS):

At the enrollment visit, prior informed consent the following assessments will be performed: physical examination, assessment of oedema, measurement of vital signs, blood and urine samples collection (see A. Schedule of assessments for more details). Afterwards, patients will be assessed at 6 weeks, 6 months and 12 months according to A. Following the international guidelines, at the 12 months visit patients will be clinically classified as SRNS, SDNS, or IRNS according to their medical history. Schedule of assessments: main population (incident INS).

Patient will come back to the center in case of relapse (see definitions) to perform the ‘first relapse visit’ according to A. Schedule of assessments: main population (incident INS).

Population 2 (control group):

This population will perform after informed consent only the enrollment visit, according to B. Schedule of assessments: control group.

Population 3 (validation cohort):

Patient will be enrolled after informed consent at relapse (enrolment visit). During this visit, a physical examination, assessment of oedema, measurement of vital signs and collection of blood and urine samples will be performed according to C. Schedule of assessments: validation cohort. At the remission (see definitions), patients will come back to the center to perform the remission visit according to C. Schedule of assessments: validation cohort.

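### Section 15.1 assigns mixed models for repeated data and a mixed-model LASSO to a primary objective of prediction at onset, and limits no selection step to enrolment samples

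*Protocol*

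**What the plan says.** Protocol section 7 gives the primary objective as the "generation of a predictive model to differentiate children with SRNS or SDNS from patients with IRNS at the onset". Section 8.2 words the endpoint as signatures "predictive of the progression of INS, which would be able to discriminate among SRNS/SDNS and IRNS groups", without a sampling time. Under section 10.1, "at the 12 months visit patients will be clinically classified as SRNS, SDNS, or IRNS according to their medical history", so each child has one class.

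Section 15.1 carries the heading for the primary endpoint and names three methods:

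- Linear mixed models: "Statistical analysis using linear mixed effect models will ensure that data from the same individuals over time are properly considered". Section 17 repeats this sentence as a general remark.
- A mixed-model LASSO: "Network-based analysis using a linear mixed effect model LASSO implementation will allow us to identify key features associated with various clinical endpoints". This sentence appears nowhere else.
- A selector working across all omics for feature subsets "associated with disease progression and treatment response, we will use a genetic algorithm-based feature selection approach".

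None of the three is tied to enrolment samples, and 15.1 mentions neither onset nor the SRNS/SDNS versus IRNS contrast.

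The nearest text to a restriction is in section 8.1: "At enrolment urine and blood samples will be collected as for normal clinical practice for the planned analysis". The same section also plans further samples according to the flowchart. Schedule A takes serum and urine for molecular work at enrolment, 6 weeks, 6 months, 12 months and first relapse. Mononuclear cells are taken at the same points except 6 months, and genetic blood at enrolment only. Children enter untreated; inclusion criterion 2 in section 9.1 reads "No previous treatment for INS".

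**The concern.** A model for use at onset has, for each child, one set of enrolment measurements and one categorical outcome. Nothing is repeated within the child, so a model for repeated measurements has no role unless later samples are brought in. A linear mixed model also takes a continuous response, whereas the target here is a class.

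Later samples differ in kind from enrolment samples. Enrolment samples are untreated; later ones are taken after treatment has begun. The first-relapse sample exists only in children who relapse, and relapse history feeds the 12-month class. A feature chosen from such samples may separate the groups through drug exposure or disease activity and say little at onset. If that happened, the signature would answer a different question from the one in section 7.

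**Working it through.** **Fit of method to objective.** The protocol gives no figure to reproduce here: section 13 sets the 110 children by feasibility and states no error rate, power or effect size. The check is therefore a comparison of sections.

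| Item | Onset objective (sections 7, 10.1) | Section 15.1 |
|---|---|---|
| Time of predictors | Onset | Not stated; first sentence concerns data over time |
| Records per child | One | Repeated data for the mixed models; not stated for the selection steps |
| Outcome | One class, assigned at 12 months | Various clinical endpoints, progression, treatment response |

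**How many scheduled samples are later ones.** Inputs: 110 children (sections 8.1 and 13) and the Schedule A visit columns. With k later visits per child, the post-enrolment share is 110k / (110 + 110k).

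The 6-week column has a footnote confining something to children not in remission at week 4. It may apply to the visit or only to the steroid pulses named in the column heading, and section 10.1 reads as if every child attends. Both limits are shown, without first-relapse samples.

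| Sample | No child has the 6-week visit | Every child has it |
|---|---|---|
| Serum (urine identical) | k = 2: 220/330 = 67% | k = 3: 330/440 = 75% |
| Mononuclear cells | k = 1: 110/220 = 50% | k = 2: 220/330 = 67% |
| Genetic blood | 0/110 = 0% | 0/110 = 0% |

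First-relapse samples raise these shares. At the extreme, with every child relapsing and every child having the 6-week visit, serum or urine reaches 440/550 = 80% and mononuclear cells 330/440 = 75%. These are scheduled samples, not rows known to be analysed.

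**What pooling visits could do.** This is an illustration only, and every input is assumed: 44 versus 66 children, 300 features, 10 features with a 0.6 SD class difference at all visits, four visits, within-child correlation 0.5, and 300 replicates. The top 10 features are chosen on the class difference, either averaged over visits or at enrolment only, and then tested on onset samples from new children. Some features that carry no signal at onset are given a class difference after enrolment.

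| Features shifted after enrolment | Onset AUC, visits pooled | Onset AUC, enrolment only |
|---|---|---|
| None | 0.87 | 0.82 |
| 30, by 0.5 SD | 0.79 | 0.82 |
| 30, by 1.0 SD | 0.54 | 0.82 |
| 10, by 0.5 SD | 0.84 | 0.82 |
| 10, by 1.0 SD | 0.66 | 0.82 |

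Pooling helps when features are stable and harms clearly only when shifts are large. The protocol does not allow a choice between these cases, and none of these AUCs is a trial figure.

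**The case against.** The strongest reply is that much of this is an omission that a SAP would fill. Section 7 states the time of prediction, section 8.1 links the enrolment samples to the planned analysis, and nothing says that later samples enter the onset model. The mixed-model sentence may be boilerplate, since section 17 repeats it. Part of this stands: 15.1 permits later samples but does not prescribe them. It does not dispose of the point, because the protocol is not silent. It names methods under the primary-endpoint heading that fit the stated objective badly.

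A reader might infer that a mixed-model LASSO must use repeated visits. The documents do not support that. Its sentence mentions no visits, and in a multicentre study the random effects could represent centre.

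A reader might also infer that features from the mixed models are what goes forward to the larger cohort. Section 15.1 speaks of feature subsets at that step, and the term most naturally refers to the output of the genetic-algorithm selector, which can run on enrolment data alone. That selector is not limited to enrolment data either, so the gap remains but the link to the two mixed-model methods is not shown.

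Finally, 15.1 also covers progression and treatment response, for which repeated data are legitimate, and a mixed model with class-by-visit terms could isolate the enrolment contrast. Both are true; 15.1 specifies no such terms.

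**Conclusion.** The point holds as a mismatch between a stated method and the primary objective, with a resulting risk that treated or relapse-only samples enter an onset signature. It should be fixed, and confidence is moderate.

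The size of the effect cannot be derived from the protocol. What can be derived is exposure: 67% to 75% of scheduled serum or urine samples and 50% to 67% of mononuclear-cell samples come after enrolment. These shares assume that all 110 children complete the other scheduled visits, and they exclude first-relapse samples. Genetic blood is unaffected.

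It would go too far to say that the signature will be contaminated, or that three quarters of the data behind it will be post-treatment. Section 15.1 does not say which samples are used, 75% is the upper limit before first-relapse samples, and a share of samples does not measure bias. The illustration gives either sign.

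**What to change.** State in section 15.1 that the primary predictive signature uses only enrolment-sample omics, genetic and clinical features, with one row per child and the 12-month class as a categorical outcome. It can be fitted with the genetic-algorithm selector already named, linked to a classifier, or with penalised logistic regression. Keep the mixed models and the mixed-model LASSO for secondary trajectory analyses.

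The outcome needs one reconciliation first. Section 8.1 groups frequent relapsers with steroid-dependent children at 12 months, whereas sections 7, 8.2 and 10.1 do not mention them. The sections should agree on where these children fall in the SRNS/SDNS versus IRNS contrast. The 6-week footnote in Schedule A should also say whether it governs the visit or only the pulses.

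The cost is wording and no new samples. The primary model would have at most 110 rows per assay, instead of up to 440 scheduled for serum or urine and 330 for mononuclear cells, with some loss of precision if features are stable over time. The change does not settle validation: the prevalent cohort is sampled at relapse and remission (section 10.1) and is not required to be untreated (section 9.3), so it offers no direct counterpart to untreated onset samples.
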